6.7. Management of IP-related Toxicities

6.7.1. **Dose Management**

Either treatment may be stopped by the investigator while the other treatment continues. MEDI0457 doses should not be modified.

For AEs that are considered at least partly due to administration of durvalumab the following dose adjustment guidance may be applied:

- Treat each of the toxicities with maximum supportive care (including holding durvalumab).
- If the symptoms promptly resolve with supportive care, consideration should be given to continuing the same dose of durvalumab along with appropriate continuing supportive care. If medically appropriate, dose modifications are permitted for durvalumab.
- All dose modifications should be documented with clear medical reasoning and documentation of the approach taken.

In addition, there are certain circumstances in which durvalumab should be permanently discontinued (Appendix D, Postow 2015).

Following the first dose of durvalumab, subsequent administration of durvalumab can be modified based on toxicities observed (Appendix D, Postow 2015). All toxicities will be graded according to NCI CTCAE version 4.03.

Based on the mechanism of action of durvalumab leading to T-cell activation and proliferation, there is the possibility of observing irAEs during the conduct of this study. Potential irAEs include immune-mediated dermatitis, hepatitis/hepatotoxicity, endocrinopathy (hypothyroidism, hyperthyroidism, hypophysitis, and adrenal insufficiency), neuropathy/neuromuscular toxicity, nephritis, pancreatitis (elevated lipase/amylase), pneumonitis, and colitis. Patients should be monitored for signs and symptoms of irAEs. In the absence of an alternate etiology (e.g., infection or PD) signs or symptoms of dermatitis, hepatitis/hepatotoxicity, endocrinopathy

Version Number: 1.8

Proprietary of MD Anderson Cancer Center Date: July 26, 2019

(hypothyroidism, hyperthyroidism, hypophysitis, and adrenal insufficiency), neuropathy/neuromuscular toxicity, nephritis, pancreatitis (elevated lipase/amylase), pneumonitis, and colitis should be considered to be immune-related.

Dose modifications will not be required for AEs that are clearly not attributable to durvalumab (such as an accident) or for laboratory abnormalities that are not deemed to be clinically significant. Administration may continue despite concurrent vitiligo of any AE grade.

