7.6.5. Hy's Law

Cases where a patient shows elevations in liver biochemistry may require further evaluation and occurrences of AST or ALT \geq 3 x ULN together with TBL \geq 2 x ULN may need to be reported as SAEs. Please refer to Appendix B for further instruction on cases of increases in liver biochemistry and evaluation of Hy's Law (HL).

7.6.6. **Events requiring reporting within 72 hours**

The following events must be reported to MDACC IND Office and supporting companies within 72 hours of the occurrence of the event to discuss whether further administration should continue for the participant.

- Grade 3 or greater injection site reaction.
- Grade 3 or greater fever, not associated with above listed events (a to f) in Section 6.7.2, assessed by Principal Investigator as related to study treatment.
- Grade 3 or greater systemic symptoms, not associated with above listed events (a to e) in Section 6.7.2, assessed by Principal Investigator as related to study treatment.

STATISTICAL ANALYSES 8.

8.1. **Statistical Considerations**

Summary statistics will be provided to summarize response, toxicity, and other clinical and demographic variables. Objective response rate and disease control rate by RECIST 1.1 criteria will be estimated with 95% confidence interval. Progression free survival and OS will be summarized using the method of Kaplan and Meier and Cox proportional hazards models. All analysis will be done across all cohorts along with subset analysis within each cohort.

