During the course of the study the investigator will remain vigilant for increases in liver biochemistry. The investigator is responsible for determining whether a patient meets potential Hy's Law (PHL) criteria at any point during the study.

The investigator participates in review and assessment of cases meeting PHL criteria to agree whether Hy's Law (HL) criteria are met. Hy's Law criteria are met if there is no alternative explanation for the elevations in liver biochemistry other than Drug Induced Liver Injury (DILI) caused by the IP.

The investigator is responsible for recording data pertaining to PHL/HL cases and for reporting adverse events (AEs) and serious adverse events (SAEs) according to the outcome of the review and assessment in line with standard safety reporting processes.

Definitions

Potential Hy's Law

A PHL case is defined as a study patient with an increase in serum aspartate aminotransferase (AST) or alanine aminotransferase (ALT) ≥ 3 x upper limit of normal (ULN) together with total bilirubin (TBL) ≥ 2 x ULN, irrespective of an increase in alkaline phosphatase (ALP), at any point during the study following the start of study medication.

Hy's Law

A HL case is defined as a study patient with an increase in serum AST or ALT \geq 3 x ULN together with TBL ≥ 2 x ULN, where no other reason, other than the IP, can be found to explain the combination of increases, e.g., elevated ALP indicating cholestasis, viral hepatitis, another drug.

For PHL and HL, the elevation in transaminases must precede or be coincident with (i.e., on the same day) the elevation in TBL, but there is no specified timeframe within which the elevations in transaminases and TBL must occur.

Identification of Potential Hy's Law Cases

In order to identify cases of PHL, it is important to perform a comprehensive review of laboratory data for any patient who meets any of the following identification criteria in isolation or in combination:

 $ALT \ge 3 \times ULN$

 $AST \ge 3 \times ULN$

Version Number: 1.8 Date: July 26, 2019 Proprietary of MD Anderson Cancer Center

 $TBL > 2 \times ULN$

When a patient meets any of the identification criteria, in isolation or in combination, the central laboratory will immediately send an alert to the investigator.

The investigator will also remain vigilant for any local laboratory reports where the identification criteria are met, where this is the case the investigator will:

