The instructions in this Section should be followed for all cases where PHL criteria are met.

No later than 3 weeks after the biochemistry abnormality was initially detected, the Study Physician contacts the investigator in order to review available data and agree on whether there is an alternative explanation for meeting PHL criteria other than DILI caused by the IP.

According to the outcome of the review and assessment, the investigator will follow the instructions below.

If there is an agreed alternative explanation for the ALT or AST and TBL elevations, a determination of whether the alternative explanation is an AE will be made and subsequently whether the AE meets the criteria for an SAE:

If the alternative explanation is **not** an AE, record the alternative explanation database.

If the alternative explanation is an AE/SAE, record the AE/SAE in the database accordingly.

If it is agreed that there is **no** explanation that would explain the ALT or AST and TBL elevations other than the IP:

Report an SAE (report term 'Hy's Law') according to MD Anderson IRB/DSMB standard processes.

The 'Medically Important' serious criterion should be used if no other serious criteria apply.

As there is no alternative explanation for the HL case, a causality assessment of 'related' should be assigned.

If, there is an unavoidable delay, of over 3 weeks, in obtaining the information necessary to assess whether or not the case meets the criteria for HL, then it is assumed that there is no alternative explanation until such time as an informed decision can be made:

Version Number: 1.8 Date: July 26, 2019 Proprietary of MD Anderson Cancer Center

Report an SAE (report term 'Potential Hy's Law') applying serious criteria and causality assessment as per above.

Continue follow-up and review according to agreed plan. Once the necessary supplementary information is obtained, repeat the review and assessment to determine whether HL criteria are met. Update the SAE report according to the outcome of the review.

Actions Required When Potential Hy's Law Criteria are Met Before and After Starting **Study Treatment**

This section is applicable to patients with liver metastases who meet PHL criteria on study treatment having previously met PHL criteria at a study visit prior to starting study treatment.

At the first on study treatment occurrence of PHL criteria being met the investigator will:

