Determine if there has been a significant change in the patients' condition[#] compared with the last visit where PHL criteria were met#

If there is no significant change no action is required

[#] A 'significant' change in the patient's condition refers to a clinically relevant change in any of the individual liver biochemistry parameters (ALT, AST or TBL) in isolation or in combination, or a clinically relevant change in associated symptoms. The determination of whether there has been a significant change will be at the discretion of the investigator, this may be in consultation with the Study Physician if there is any uncertainty.

Actions Required for Repeat Episodes of Potential Hy's Law

This section is applicable when a patient meets PHL criteria on study treatment and has already met PHL criteria at a previous on study treatment visit.

The requirement to conduct follow-up, review and assessment of a repeat occurrence(s) of PHL is based on the nature of the alternative cause identified for the previous occurrence.

The investigator should determine the cause for the previous occurrence of PHL criteria being met and answer the following question:

Was the alternative cause for the previous occurrence of PHL criteria being met found to be the disease under study e.g., chronic or progressing malignant disease, severe infection or liver disease, or did the patient meet PHL criteria prior to starting study treatment and at their first on study treatment visit as described in Actions Required When Potential Hy's Law Criteria are Met Before and After Starting Study Treatment?

If Yes:

Version Number: 1.8 Date: July 26, 2019

Proprietary of MD Anderson Cancer Center

Determine if there has been a significant change in the patient's condition[#] compared with when PHL criteria were previously met

If there is no significant change no action is required.

If there is a significant change follow the process described in **Appendix D**, **Table 7**.

[#] A 'significant' change in the patient's condition refers to a clinically relevant change in any of the individual liver biochemistry parameters (ALT, AST or TBL) in isolation or in combination, or a clinically relevant change in associated symptoms. The determination of whether there has been a significant change will be at the discretion of the investigator; this may be in consultation with the Study Physician if there is any uncertainty.

References

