function tests [LFTs]) Infliximab should not be used for management of immune-related hepatitis	elevation (CTCAE version 4.03) Any grade Grade 1 (AST or ALT > upper limit of normal [ULN] to 3 times ULN and/or TBL > ULN to 1.5 times ULN)	No dose modification. If it worsens, treat as Grade 2 event.	 alkaline phosphatase (ALP), and total bilirubin (TBL) Evaluate for alternative etiologies (e.g., viral hepatitis, disease progression, concomitant medications). For Grade 1 AST or ALT and/or TBL elevation Continue LFT monitoring per protocol.
	Grade 2 (AST or ALT > 3 to 5 times ULN and/or TBL > 1.5-3.0 times ULN)	 Hold study drug/study regimen dose until Grade 2 resolution to ≤ Grade 1 If toxicity worsens then treat as Grade 3 or Grade 4 Study drug/study treatment can be resumed based upon treating physician's clinical judgment at the next scheduled dose once event stabilizes to Grade ≤ 1 or baseline and 5-7 days have passed after completion of steroid taper. 	 For Grade 2 AST or ALT and or TBL elevation: Regular and frequent checking of LFTs (e.g., every 1-2 days) until elevations of these are improving or resolved. If no resolution to ≤ Grade 1 in 1-2 days, discuss with Study Physician. If event is persistent (> 3-5 days) or worsens, promptly start prednisone 1-2 mg/kg/day or IV equivalent. If still no improvement within 3-5 days despite 1-2 mg/kg/day of prednisone or IV equivalent, consider additional work-up and prompt treatment with IV methylprednisolone 2-4 mg/kg/day started. If still no improvement within 3-5 days despite 2-4 mg/kg/day of IV methylprednisolone, promptly start immunosuppressives (mycophenolate mofetil)⁴. Discuss with Study Physician if mycophenolate mofetil is not available. Infliximab should NOT be used. Once improving, gradually taper steroids over ≥ 28 days and consider prophylactic antibiotics, antifungals and anti PCP treatment (please refer to current NCCN guidelines for treatment of cancer-related infections [Category 2B recommendation]).
	Grade 3 (AST or ALT > 5-20 times ULN and/or TBL > 3.0-10 times ULN	 For elevations in transaminases ≤ 8 × ULN, or elevations in bilirubin ≤ 5 × ULN Hold study drug/study regimen dose until resolution to ≤ Grade 1 or baseline 	 For Grade 3 or 4 AST or ALT and/or TBL elevation: Promptly initiate empiric IV methylprednisolone at 1 to 4 mg/kg/day or equivalent. If still no improvement within 3-5 days despite 1 to 4 mg/kg/day methylprednisolone IV or equivalent,

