⁴ ASCO Educational Book 2015 "Managing Immune Checkpoint Blocking Antibody Side Effects", by Michael Postow MD

Version Number: 1.8
Date: July 26, 2019

Proprietary of MD Anderson Cancer Center

Date: July 26, 2019		1 7	
	Grade 4 (AST or ALT > 20 times ULN and/or TBL > 10 times ULN)	 Resume study drug/study regimen administration at the next scheduled dose if elevations downgrade ≤ Grade 1 or baseline Permanently discontinue study drug/study regimen if the elevations do not downgrade to ≤ Grade 1 For elevations in transaminases > 8 × ULN or elevations in bilirubin > 5 × ULN, discontinue study drug/study regimen Permanently discontinue study drug/study regimen for any case meeting Hy's Law criteria (ALT > 3 × ULN + bilirubin > 2 × ULN without initial findings of cholestasis (i.e., elevated alkaline P04) and in the absence of any alternative cause⁵ Permanently discontinue study drug/study regimen. 	promptly start treatment with immunosuppressive therapy (mycophenolate mofetil). Discuss with Study Physician if mycophenolate is not available. Infliximab should NOT be used. - Hepatology consult, abdominal work-up, and imaging as appropriate. - Once improving, gradually taper steroids over ≥ 28 days and consider prophylactic antibiotics, antifungals and anti PCP treatment (please refer to current NCCN guidelines for treatment of cancer-related infections [Category 2B recommendation]).
Nephritis or renal dysfunction (elevated serum creatinine)	Grade of elevated serum creatinine (CTCAE version 4.03) Any grade Grade 1 [serum	No dose modification	 Consult with nephrologist. Monitor for signs and symptoms that may be related to changes in renal function (e.g., routine urinalysis, elevated serum blood urea nitrogen and creatinine, decreased creatinine clearance, electrolyte imbalance, decrease in urine output, proteinuria, etc). Subjects should be thoroughly evaluated to rule out any alternative etiology (e.g., disease progression, infections etc). Steroids should be considered in the absence of clear alternative etiology even for low grade events (Grade 2), in order to prevent potential progression to higher grade event. For Grade 1 elevated creatinine:
	creatinine > 1-1.5 × baseline; > ULN to 1.5 × ULN]	140 dose modification	 Monitor serum creatinine weekly and any accompanying symptom If creatinine returns to baseline, resume its regular monitoring per study protocol.

-

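### Table 7's Hy's Law stop line names ALT only, with strict inequalities, and so conflicts with the AST-or-ALT definition in Appendix B and Section 7.6.5

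*Combined protocol and SAP*

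**What the plan says.** Three places set Hy's Law thresholds.

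- **Appendix B, Definitions:** "A HL case is defined as a study patient with an increase in serum AST or ALT" of at least 3 x ULN together with TBL of at least 2 x ULN, with no explanation other than the study drug. A confirmed case is reported as an SAE, and "As there is no alternative explanation for the HL case, a causality assessment of 'related' should be assigned". Appendix B gives no instruction to discontinue.
- **Section 7.6.5:** "Cases where a patient shows elevations in liver biochemistry may require further evaluation and occurrences of AST or ALT" of at least 3 x ULN with TBL of at least 2 x ULN may be reportable as SAEs. It refers the reader to Appendix B for evaluation.
- **Appendix D, Table 7, hepatitis entry:** "Permanently discontinue study drug/study regimen for any case meeting Hy's Law criteria (ALT > 3 × ULN + bilirubin > 2 × ULN", qualified by "without initial findings of cholestasis (i.e., elevated alkaline P04) and in the absence of any alternative cause". This is the only line that makes a permanent stop mandatory for Hy's Law. Its footnote cites an FDA guidance, not Appendix B.

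On dosing, Section 6.7.1 points to the same appendix: "In addition, there are certain circumstances in which durvalumab should be permanently discontinued (Appendix D". For some repeat episodes Appendix B does so too: "If there is a significant change follow the process described in" Table 7.

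Table 7's Grade 2 row (AST or ALT above 3 to 5, TBL above 1.5 to 3 x ULN) holds the drug and then allows a restart: "Study drug/study treatment can be resumed based upon treating physician's clinical judgment at the next scheduled dose". Its Grade 3 text holds the drug at transaminases up to 8 or bilirubin up to 5 x ULN and resumes it on recovery to Grade 1 or baseline. Above 8 or 5 x ULN it discontinues.

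**The concern.** The dosing table and the definition differ in two ways. The table's bracket omits AST, and it uses strict inequalities where Appendix B includes the threshold itself. The omission of AST is the one that matters. The other hepatitis rows of Table 7 speak of AST or ALT, or of transaminases, so ALT alone is peculiar to the Hy's Law line.

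Two readings are open. If the words referring to any case that meets Hy's Law criteria import Appendix B, the bracket is loose shorthand and nothing is lost. If the bracket is the criterion, an AST-driven case can be a drug-related Hy's Law SAE under Appendix B and yet fall under hold-and-resume text in the dosing table. Table 7 does not say which reading applies.

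AST is not incidental here. In the pooled durvalumab monotherapy data (Section 1.2.2, 1645 patients), Grade 3 AST increase was reported in 1.6% and Grade 3 ALT increase in 1.1%. These are not Hy's Law counts. They show only that a liver stop rule in this trial should not leave AST out.

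**Working it through.** There is no stated figure to reproduce. The check applies each rule, as written, to the same liver profiles.

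**Rules (values in x ULN; no cholestasis, no other cause, no Gilbert's syndrome)**

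- Appendix B and 7.6.5: (AST ≥ 3 or ALT ≥ 3) and TBL ≥ 2.
- Table 7 Hy's Law line, literal bracket: ALT > 3 and TBL > 2.
- Table 7 upper line: AST or ALT > 8, or TBL > 5.
- Section 7.6.4 trigger, from the limits in inclusion criterion 8: AST or ALT > 3, or TBL > 1.5.
- DLT item i (Section 6.7.2): AST or ALT > 8, or TBL > 5.

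| AST / ALT / TBL | Appendix B Hy's Law | Table 7, literal bracket |
|---|---|---|
| 4 / 2 / 2.5 | yes | Grade 2: hold, may resume |
| 6 / 2 / 2.5 | yes | Grade 3: hold, resume on recovery |
| 8 / 3 / 5 | yes | Grade 3: hold, resume on recovery |
| 3 / 3 / 2.0 | yes | Grade 2: hold, may resume (exact threshold only) |
| 2 / 4 / 2.5 | yes | stopped by the Hy's Law line |
| 9 / 2 / 2.5 | yes | stopped by the > 8 line |
| 6 / 2 / 6 | yes | stopped by the > 5 line |

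**Bounds.** The literal gap is AST about 3 to 8, ALT ≤ 3 and TBL about 2 to 5.

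**Grid check.** Steps of 0.1 were used, with AST and ALT from 0 to 10 and TBL from 0 to 7.

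- At TBL = 2.0: 81 x 81 - 30 x 30 = 5,661 gap cells.
- At TBL 2.1 to 5.0: 30 x (81 + 30 x 51) = 48,330.
- Total: 53,991. Of these, 50 x 31 x 30 = 46,500 are AST-driven (AST > 3, ALT ≤ 3, TBL > 2). The other 7,491 exist only because a value sits exactly on a threshold.
- All 53,991 trigger Section 7.6.4, because TBL ≥ 2 exceeds 1.5. None meets DLT item i. None remains if Table 7 uses the Appendix B thresholds.

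Cell counts describe the rule. They say nothing about how many patients would be affected.

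**Other DLT items.** These can catch only the Grade 3 part of the gap (AST > 5 or TBL > 3), and only in the 4 weeks after the first durvalumab dose. That is 4 / (13 x 4) = 7.7% of a full 13-dose course.

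**Placement of the line.** The table row is broken in the text available, but the Hy's Law line appears to sit among the Grade 3 bullets. Applying it to the Grade 2 profile 2 / 4 / 2.5 therefore rests on its opening words, which cover any case. If it were confined to Grade 3, ALT-driven Grade 2 profiles would also escape it, and the bounds above would be too narrow.

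**The case against.** The strongest reply is that no patient would be restarted.

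- Table 7's operative words refer to Hy's Law criteria. Appendix B defines that term, and Section 7.6.5 names Appendix B as the place to evaluate it.
- Section 7.6.4 requires immediate interruption when no definitive underlying diagnosis is found. Its only stated basis for continued dosing is a definitive diagnosis unrelated to study drug, which a Hy's Law case by definition lacks.
- Under Section 3.4 the investigator, the supporting company or the IND Office can each stop dosing. Under Appendix B the Study Physician must agree the follow-up.
- It is also selective to read the bracket literally while reading the line's position in the table by its purpose.

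Most of this stands, and it is why the point is minor. A reader might infer that the protocol permits re-exposure after confirmed AST-driven drug-induced liver injury. The documents do not support that. A restart would need the bracket read literally, Appendix B's definition set aside, and the 7.6.4 interruption treated as lifted without the one condition that section gives.

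What survives is narrower. Section 7.6.4 requires interruption, not permanent discontinuation, and does not say how it relates to Table 7's resume rows. Appendix B orders a report, not a stop. The 3.4 and Study Physician controls rest on judgement. So the only mandatory permanent stop for Hy's Law carries a criterion that conflicts with the protocol's own definition.

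**Conclusion.** The inconsistency is real, and the Table 7 line is wrong as written. Severity is minor. On the literal reading, the cases left without a mandatory permanent stop are those with AST about 3 to 8, ALT ≤ 3 and TBL about 2 to 5 x ULN, no cholestasis and no other cause. This bound assumes that the line applies at every grade. The difference between the strict and inclusive inequalities is trivial for continuous values.

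The documents give no Hy's Law count, so the number of patients cannot be estimated. I assume it is few among up to 77 evaluable patients. Section 7.6.4 interrupts dosing in every such case. The ORR analysis is unaffected. Confidence is high in the textual conflict. Whether any site would act on the literal reading is uncertain and looks unlikely.

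**What to change.** In the Table 7 Hy's Law line, replace the bracketed thresholds with *AST or ALT ≥ 3 x ULN together with TBL ≥ 2 x ULN, as defined in Appendix B*. Keep both existing conditions: no initial cholestasis and no alternative cause. Add that the line applies at any CTCAE grade and overrides the hold-and-resume text.

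The cost is a few words in one table at the next amendment. No new tests are needed, because AST, ALT, alkaline phosphatase and total bilirubin are already in the chemistry panel (Table 3 footnotes). The downside is that a few patients who might have tolerated a restart would stop permanently.
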